## 9.0 MONITORING

This study will engage multiple users who will be observed by the Sponsor's clinical engineering staff. Therefore, there will be minimal third-party monitoring of this small study.

## 10.0 REGULATORY REQUIREMENTS

This study is conducted under the requirements set forth by CFR 21 Part 812, 21CFR Part 50 (Informed Consent), and 21CFR Part 56 (IRB Review).

### PERSONNEL RESPONSIBILITIES

#### *Principal Investigator Responsibilities*

- a) Permit Sponsor/Monitor inspection of facilities and records
- b) Permit inspection of facilities and records by government bodies
- c) Submit protocol and informed consent to IRB and await approval
- d) Submit proposed amendments to protocol and informed consent to IRB and await approval
- e) Obtain informed consent of participants
- f) Implement study in accordance with protocol
- g) Complete CRFs/questionnaires and ensure all other users do the same
- h) Explain deviations from protocol and report to monitor
- i) Submit annual progress reports, final reports, and adverse effect reports to IRB and Sponsor
- j) Record the receipt, disposition, and return of devices
- k) Retain records for a minimum of two years following study completion (refer to IRB rules)

#### *Sponsor Responsibilities*

- a) Assure IRB approval of protocol and informed consent is obtained
- b) Select and train Monitors as needed
- c) Select Sites and Investigators
- d) Train Investigators in device use
- e) Obtain curriculum vitae and proof of appropriate licensure of Investigators and study staff
- f) Control shipment of devices
- g) Investigate device-related adverse events
- h) Maintain responsibility for data review and analysis
- i) Obtain statement of financial disclosure for publication and presentation purposes

**APPENDIX 1**  
**DEVICE USE QUESTIONNAIRE**

Surgeon Name: \_\_\_\_\_

Obstetrician

Fellow

Resident (Circle one)

Years of experience in Obstetrical Surgery: \_\_\_\_\_

Date of Evaluation: \_\_\_\_\_ Placement #: 1 2 3 (Circle One)

Type of Suction Tube used (Brand & ID): \_\_\_\_\_

This Questionnaire aims to evaluate a set of aspects related to the use of the Daisy® device by the personnel in attendance. You are asked to indicate your level of agreement for each of the questions posed below, according to the scale of responses, place a check mark in the appropriate box.

	Strongly Agree	Agree	Neutral	Disagree	Strongly Disagree
Device training clearly explained insertion, use and removal of the device.					
The Instructions for Use (IFU) are clear and concise.					
The Daisy was easy to insert through the cervix.					
The Daisy was easy to properly position within the uterus.					
The Daisy was easily visualized in the lower uterine segment at time of placement.					
The Tube of the Daisy was easily advanced through the vaginal canal.					
The Cap of the Daisy was easily identified & retrieved outside the introitus.					
The Cap of the Daisy was easy to remove from the Tube.					
The Cap of the Daisy had adequate retention in the Tube.					
The Daisy did not interfere with the closure of the hysterotomy incision.					
The Daisy Tube fits easily into standard suction tubing.					

The suction tubing was easy to secure to the leg of the participant using the provided adhesive Catheter Anchors.					
The Daisy remained in place until elective removal.					
The estimated blood loss from the uterus was easy to determine.					
Use of the Daisy did not interfere with routine OR or PACU practices.					
The force to remove the Daisy was acceptable.					
Overall, the Daisy was easy to use.					
The Daisy drained without intervention (clot removal). Describe any clots or interventions in the Comments below.					
Blood flow was easy to visualize through the Tube.					
Overall, the Daisy met all the user needs as intended.					

Other comments regarding the use of the Daisy: \_\_\_\_\_

\_\_\_\_\_

\_\_\_\_\_

\_\_\_\_\_

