## **METHODS**

### *User Training:*

Minimal product training is necessary other than a review of the IFU. Company personnel will initially observe the insertion and removal procedures and secure feedback post placement and removal to be sure that the IFU is clear and appropriately informative.

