## **8.0 DATA MANAGEMENT AND STATISTICAL ANALYSIS**

The data collected will be marked with a study ID number to protect the confidentiality of each Participant. Only the research staff will have access to the link between the study ID and the patient's identifying information. The key will be stored in a password-protected document on a restricted access folder on the hospital network. Only the Principal Investigator, Sub-Investigator, and research team will have access to this document. This document will contain the participants' de-identified obstetric and medical history as relevant for the project.

Third-party data management and statistical analysis of de-identified data may be used. Analysis of the user responses will consist primarily of means, medians, and standard deviations. To accomplish this, the following points will be assigned to user responses.

Strongly Disagree 1 point	Disagree 2 points	Neutral 3 points	Agree 4 points	Strongly Agree 5 points
------------------------------	----------------------	---------------------	-------------------	----------------------------

The Sponsor will follow up with any responses where the user has "disagreed" or "strongly disagreed" with the statement.

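### Two questionnaire items each combine different stages of use in one rating, so a mixed experience may escape the Sponsor's follow-up and cannot be traced to a stage

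*Protocol*

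**What the plan says.** The Device Use Questionnaire (Protocol, Appendix 1) has 20 statements, each rated once from Strongly Agree to Strongly Disagree. Two of them cover more than one stage of use:

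- "Use of the Daisy did not interfere with routine OR or PACU practices"
- "Device training clearly explained insertion, use and removal of the device"

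Two others join closely related attributes: "The Instructions for Use (IFU) are clear and concise" and "The Cap of the Daisy was easily identified & retrieved outside the introitus".

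Section 8.0 scores the responses from 1 (Strongly Disagree) to 5 (Strongly Agree) and states: "Analysis of the user responses will consist primarily of means, medians, and standard deviations". On individual answers it says "The Sponsor will follow up with any responses where the user has" chosen one of the two lowest categories. It makes no commitment for Neutral, Agree or Strongly Agree.

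There are other routes by which a problem could surface. The form ends with a free-text field, "Other comments regarding the use of the Daisy". Section 6.0 (User Training) says "Company personnel will initially observe the insertion and removal procedures and secure feedback post placement and removal", to check that the Instructions for Use (IFU) are clear. Section 9.0 says that the Sponsor's clinical engineering staff will observe users.

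**The concern.** Section 3.0 sets out to learn how surgeons interact with the drain, how easily it is placed, what adding suction does, and whether the IFU is accurate. Section 6.0 (Test Environment) says that the study looks more at the users than at the participants. The questionnaire is therefore the main instrument, and its value lies in showing which step needs changing.

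A rating that spans two or three stages does this poorly when the stages differ. The user must decide how to combine them, and the form gives no guidance, so different users may combine them differently. If the result is Neutral or better, the follow-up rule does not apply.

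The operating-room/PACU item is the more important of the two. Placement happens in the operating room. Section 5.0 keeps the drain under suction for at least the first two hours after delivery and has the drain in place in the recovery unit, with repeated palpation and three ultrasounds. Suction is the element that this study adds, and interference with recovery-unit routine is asked about only in this shared item.

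**Working it through.** The protocol states no figure on this point, so there is none to reproduce. The check is a count of items, followed by the Section 8.0 rule applied to assumed answers.

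**Count of items (Appendix 1).**

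- Rated statements: 20.
- Statements joining more than one attribute: 4 (training, IFU, Cap, operating room/PACU), which is 4/20 = 20%.
- Of these, statements joining substantively different stages: 2 (operating room/PACU with two parts, training with three), which is 2/20 = 10%.

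**What the follow-up rule catches (Section 8.0).** Follow-up is committed when the score is 2 or lower. Suppose that one user's experience would be rated 5 for the operating room and 2 for the PACU if asked separately. The joint item allows several answers:

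- The user reads the statement literally, finds it false and ticks Disagree: score 2, follow-up.
- The user averages the two parts: (5 + 2)/2 = 3.5, recorded as 3 or 4, no committed follow-up.

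The documents do not say which of these a user will do.

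**What the summaries show.** Assume ten forms (ten placements, one form each), nine scored 5 and one mixed:

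| Mixed form scored | Mean | Median | SD | Follow-up committed |
|---|---|---|---|---|
| 2 | (45 + 2)/10 = 4.7 | 5 | 0.95 | Yes |
| 3 | (45 + 3)/10 = 4.8 | 5 | 0.63 | No |
| 4 | (45 + 4)/10 = 4.9 | 5 | 0.32 | No |

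In all three rows the mean is high and the median is 5, so the summaries alone would not draw attention to the problem. Detection depends on the follow-up rule, and that depends on how the user resolved the mixed experience.

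**Attribution.** A joint score of 3 or 4 is the same whether the parts were 5 and 2 or 2 and 5. For training, the triples (5, 5, 2), (5, 2, 5) and (2, 5, 5) all average 12/3 = 4. The score does not identify the stage.

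**The same case with separate statements.** The operating-room statement has ten scores of 5, mean 5.0. The PACU statement has nine scores of 5 and one of 2, mean 4.7. The score of 2 triggers follow-up under the existing rule, and the stage is known.

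**Other items that touch recovery.** The form separately rates whether the drain stayed in place, whether it drained without intervention, how easily blood loss could be determined and the removal force. These concern the device's performance. None asks whether its use disrupted PACU routine.

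**The case against.** A reader might infer that a mixed experience will be scored Neutral or Agree and stay hidden, or that such a user has no correct answer. The documents do not support that. Read literally, the operating-room/PACU statement is false if either setting was disrupted, and the training statement fails if any stage was poorly explained. A literal reader would tick Disagree, which triggers follow-up. Averaging is an assumption about behaviour, not something the protocol says. This objection stands, and it limits the point to what may happen.

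A reader might also infer that a missed problem could not be recovered in any other way. That is too strong. There is a comments field, company staff observe and gather feedback, and only five named surgeons take part at one center, so any answer could be queried. Section 8.0 commits to follow-up for low scores but does not forbid it for others. The feedback in Section 6.0 is aimed at the clarity of the IFU and so bears on the training item in particular. These routes are still partial. Observation under User Training is described as initial and names insertion and removal only. Section 9.0 does not say that observation extends through the PACU stay. Only the clot item directs the user to the comments, and no review of comments is specified.

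Finally, a reader might count all four compound items as equally faulty. That overstates the scope. Clear and concise is a stock pairing about one document, and identifying and retrieving the Cap is close to one continuous action. Splitting these is a matter of wording. Most other steps, including insertion, positioning, connection and removal force, already have their own lines.

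**Conclusion.** The point holds in a limited form. Two of the 20 items join stages that can differ, the form does not say how to rate a mixed experience, and committed follow-up starts at Disagree. A problem in one stage may therefore be rated Neutral or better and miss the follow-up rule, and the score cannot show which stage was at fault. How often this would happen cannot be estimated from the protocol. The numerical illustration rests on assumed answers, and the argument about recovery takes PACU to mean the recovery unit of Section 5.0.

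The operating-room/PACU item carries most of the weight, and the training item less. The protocol contains no wrong figure or contradiction here, and the remaining 16 single-attribute items are unaffected. This is a modest improvement to the main instrument of a small descriptive study.

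**What to change.** Before the form is used, split the two items into single statements:

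- no interference with routine operating-room practice; no interference with routine PACU practice;
- training clearly explained insertion; training clearly explained use; training clearly explained removal.

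The form goes from 20 to 20 - 2 + 5 = 23 statements. Score and follow up each one under the existing Section 8.0 rule. The scale, the summaries and the clinical procedures do not change.

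The cost is three more lines per form, on about ten forms. The change has to come first, because separate ratings cannot be reconstructed from a completed joint rating. Extending follow-up to Neutral on these two items would be a weaker alternative, since it would still miss a mixed experience rated Agree. Splitting the IFU and Cap items as well is optional.

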## **APPENDIX 2**

### **PRIMARY PARTICIPANT DATA TO BE COLLECTED**

Participant ID

Inclusion/Exclusion Criteria Met (yes/no)

Date of Consent

Date of Caesarean Section/Device Use

Reason for Caesarean Section

Period of Gestation

Pre-Operative Hemoglobin and Hematocrit

Post Operative Hemoglobin and Hematocrit

Cervical Dilation

Time of Device Insertion

Level of Suction

Uterine tone at three time points Post Partum

Time of Device Removal

Total Estimated Blood Loss (EBL)

Use of Uterotonics

Postpartum Uterine Ultrasound Scale (PUUS) at three time points Post Partum

Ultrasound evaluations of device position, uterine cavity size, fundal and lower uterine segment at three time points Post Partum

Adverse Events (Visits 2 and 3)
